7.1. ADJUSTMENTS FOR COVARIATES AND FACTORS TO BE INCLUDED IN ANALYSES

The following covariates and factors will be used in the analyses. For details of their inclusion in the models, see the specific analysis section.

Covariates

- Baseline MMS
- Baseline pMMS
- Baseline Fecal Calprotectin level
- Baseline Geboes Score
- Baseline Nancy Score
- Baseline RHI

Factors

- Treatment arm (ABX464 100mg, ABX464 50 mg, ABX464 25mg, Placebo)

Document: \\iedc-vnasc01\BIOSdata\Abivax\ABX464\FZA92720\Biostatistics\Documentation\SAP\ABX464-103_SAP_V2.0_10MAY2021

Author: [REDACTED]

Version Number:

2.0

Version Date:

10May2021

Template No.: CS_TP_BS016 Revision 5

Reference: CS_WI_BS005

Effective Date: 01Apr2018

- Previous biologic or JAK inhibitors treatment use (Yes/No)

7.2. MULTICENTER STUDIES

This study will be conducted by multiple investigators at multiple centers internationally. Randomization to treatment arms is stratified by previous exposure/non-exposure to biologics and JAK inhibitors treatment use and US/non-US sites.

7.3. MISSING DATA

A subject's missing efficacy data viz. MMS (or any components of MMS missing) at Week 8, will be imputed and the subject will be considered as a non-responder for clinical remission and response.

Missing MMS components at Week 8 will be imputed as follows:

Stool Frequency Sub score: The average of the 3 recent eDiary stool frequency records (if no prior records then choose records after the Week 8 visit date) within 10 days of date of week 8 visit is calculated. The normal stool frequency (at screening) is subtracted from the average and rounded to a whole number. The imputed sub score will be assigned as follows:.

Sub score=0; if calculated value =0

Sub score=1; if calculated value=1,2

Sub score=2; if calculated value=3,4

Sub score=3; if calculated value=5 or greater

If no records available within 10 days from eDairy, the nearest neighbour method will be considered.

Rectal Bleeding Sub score: The worst of the 3 recent eDiary records within 10 days of Date of Week 8 visit, will be considered as the analysis value (if no prior records then choose records after the Week 8 visit date) . If no records available within 10 days from eDairy, the nearest neighbour method will be

Document: \\iedc-vnasc01\BIOSdata\Abivax\ABX464\FZA92720\Biostatistics\Documentation\SAP\ABX464-103_SAP_V2.0_10MAY2021

Author: [REDACTED]

Version Number:
Version Date:

2.0
10May2021

Template No.: CS_TP_BS016 Revision 5

Reference: CS_WI_BS005

Effective Date: 01Apr2018

considered.

Mucosal appearance at Endoscopy: The analysis value of the nearest neighbour is used to impute missing Endoscopy sub score. The nearest neighbour is defined as the subject in Placebo arm with non-missing sub score, matching the 'subject with missing value' by Gender, Baseline MMS, Age and Previous Exposure to other biologics/JAK status. The matching score is calculated for all the placebo subjects with non-missing sub score, as follows:

- 1) If the subject matches in gender, 5 points assigned.
- 2) If previous exposure status matches, then additional 5 points.
- 3) The absolute difference between the Baseline MMS and Age, is subtracted from the scores.

The Placebo subject with the highest score is considered the nearest neighbour. In case of tied nearest neighbour scores, the worst sub score value will be used to impute.

The imputed components will be used to derive the pMMS (Stool Frequency Sub score + Rectal Bleeding Sub score) and MMS (Stool Frequency Sub score + Rectal Bleeding Sub score + Endoscopy Sub score) at Week 8.

Missing safety data will not be imputed. Percentages based on the number of subjects with data available will not take missing observations into account.

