 - The subject must have a clinically confirmed diagnosis of moderate to severe ulcerative colitis, with an MMS score of 5 to 9 inclusive and endoscopy sub-score of at least 2. Subjects enrolled on original protocol may have a baseline MMS score of 4.

- Patients younger than 18 or older than 75 years:

CRITERION [7]: Patients Younger than 18 or older than 75 Years

DEVIATION STATUS: Major/No Major Impact, to be decided on a case-by-case basis at the final data review meeting.

NOTES:

- Age (years) as at informed consent will be used.
- This criterion will be tested using:
 - The date of birth as captured on the Demographics (DM) eCRF and obtained from raw.DM.BRTHDATZ and raw.DM.AGE.
 - The date of informed consent as captured on the DM eCRF and obtained from

Document: \\ieddc-vnasc01\BIOSdata\Abivax\ABX464\FZA92720\Biostatistics\Documentation\SAP\ABX464-103_SAP_V2.0_10MAY2021

Author: [REDACTED]

Version Number:
Version Date:

2.0
10May2021

Template No.: CS_TP_BS016 Revision 5

Reference: CS_WI_BS005

Effective Date: 01Apr2018

raw.DM.DSSTDAT_IC.

- Patients who didn't meet the required laboratory screening criteria:

CRITERION [8]: Patient Didn't Meet Laboratory Screening Criteria

DEVIATION STATUS: Major/No Major Impact, to be decided on a case-by-case basis at the final data review meeting.

NOTES:

- The patient must meet the following laboratory screening criteria:
 - Haemoglobin $> 9 \text{ g/dL}^{-1}$
 - Absolute neutrophil count $\geq 750 \text{ mm}^{-3}$
 - Platelets $\geq 100,000 \text{ mm}^{-3}$
 - Total serum creatinine $\leq 1.3 \times \text{ULN}$ (upper limit of normal)
 - Creatinine clearance $> 90 \text{ mL min}^{-1}$ by the Cockcroft-Gault equation within 60 days prior to baseline
 - Total serum bilirubin $< 1.5 \times \text{ULN}$
 - Alkaline phosphatase, aspartate aminotransferase (AST)/serum glutamic oxaloacetic transaminase (SGOT) and alanine aminotransferase (ALT)/serum glutamic pyruvate transaminase (SGPT) $< 2 \times \text{ULN}$
- This criterion will be tested using the following data:
 - Not meeting these criteria will be captured on the IE eCRF and obtained from raw.IE.IEYN, IECAT and IETESTCD.

- Patients who didn't have documented inadequate response, no response, loss of response or an intolerance to specified alternate treatments:

• CRITERION [9]: Patient Didn't have Documented Inadequate Response, No Response, Loss of Response or an Intolerance to Specified Alternate Treatments:

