15.1.2. MISSING DATA METHODS FOR PRIMARY EFFICACY VARIABLE

Subjects with missing primary efficacy values will be imputed as non-responders for clinical remission and response at Week 8. Missing MMS scores at Week 8 will be imputed as mentioned in section 7.3.

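### Step 3 of the nearest-neighbour score in SAP 7.3 takes the difference between baseline MMS and age, so as written it compares neither with the patient being imputed

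*SAP*

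**What the plan says.** SAP 7.3 takes a missing Week 8 endoscopy subscore from a nearest neighbour in the placebo arm. It defines that neighbour as a placebo subject "matching the 'subject with missing value' by Gender, Baseline MMS, Age and Previous Exposure to other biologics/JAK status". It then gives a score: "The matching score is calculated for all the placebo subjects with non-missing sub score". Step 1 gives 5 points for the same gender and step 2 gives 5 more for the same exposure status. Step 3 is: "The absolute difference between the Baseline MMS and Age, is subtracted from the scores". The highest score wins. On ties: "In case of tied nearest neighbour scores, the worst sub score value will be used to impute".

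The same method is the fallback for stool frequency and rectal bleeding: "If no records available within 10 days from eDairy, the nearest neighbour method will be considered". The results enter the scores: "The imputed components will be used to derive the pMMS", and likewise the full MMS. SAP 15.1.2 applies this to the primary variable: "Missing MMS scores at Week 8 will be imputed as mentioned in section 7.3".

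**The concern.** Steps 1 and 2 compare the donor with the patient whose value is missing. Step 3 subtracts a score from a number of years and does not say whose score or whose age is meant. Read literally, it cannot deliver the matching on MMS and age that the defining sentence promises. No formula, example or scaling elsewhere in the SAP settles it.

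At stake is a pre-specified rule for the primary endpoint. It sets every imputed Week 8 endoscopy subscore, and the two symptom subscores when no diary record lies within 10 days. Programmers who read step 3 differently would pick different donors, and an independent check could not tell which program was right.

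**Working it through.** **Inputs.** Age 18 to 75 and baseline MMS 5 to 9 (protocol 4.2.1). An MMS of 4 is also possible: "Subjects enrolled on original protocol may have a baseline MMS score of 4" (SAP 5.2.4). Match points are at most 5 + 5 = 10 (SAP 7.3). Protocol 9.4 gives the SD of MMS reduction as 2.1, the assumed effect as 2.5 - 1.0 = 1.5, 61 patients per arm, and 5% dropout for the 58-per-arm calculation. The documents state no figure for the matching rule, so there is none to reproduce.

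**Reading (a), donor's own values.** Score = match points - |MMS of donor - age of donor|.
- Smallest penalty: 18 - 9 = 9. Largest: 75 - 5 = 70, or 75 - 4 = 71 with MMS 4.
- The recipient's age and MMS never enter. Each gender-by-exposure type of recipient has one fixed winner, so apart from ties at most 4 donors are ever used.
- Example: the recipient is female, exposed, MMS 7, age 45. An identical donor scores 10 - 38 = -28. A female, exposed donor aged 18 with MMS 9 scores 10 - 9 = +1 and is chosen.
- With donor-recipient differences the same two donors score 10 - 0 - 0 = +10 and 10 - 2 - 27 = -19, so the order reverses.

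**Reading (b), recipient's own values.** The penalty is the same for every donor and cancels. Only gender and exposure count. With 58 donors, 60% of one sex and 50% exposed, the expected number of tied donors is 58 x (0.6² + 0.4²) x 0.5 = 15. The worst subscore among them is used.

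**Simulated match quality.** The documents give no distributions, so these are assumptions: 58 placebo donors, 20 recipients, 800 pools, age N(42, 14) cut at 18 to 75, MMS 5 to 9, 60% of one sex, 50% exposed. Ranges in brackets cover mean age 35 to 50, SD 10 to 14 and two MMS distributions.

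| Rule | Mean age gap, years | Mean MMS gap |
|---|---|---|
| (a) donor's values | 22 (15-26) | 1.3 (1.3-1.6) |
| (b) recipient's values | 14 (10-14) | 1.3 (1.3-1.6) |
| Random donor | 14 (10-14) | 1.3 (1.3-1.6) |
| Donor-recipient differences | 1.5 (1.3-1.6) | 0.9 (0.8-1.0) |

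A second simulation (uniform MMS; ages uniform or N(41, 14)) gave the same pattern: age gaps of 26.8 or 22.5 years for (a), 19.3 or 15.2 for a random donor, and 1.7 or 1.6 for donor-recipient differences.

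**Imputed values under (b).** The share of imputed endoscopy subscores equal to 3 depends on the assumed mean Week 8 placebo endoscopy subscore: 97% at 1.9, 84% at 1.5 and 62% at 1.2. With donor-recipient differences it is about 30% at 1.9.

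**Effect on the primary contrast.**
- Planned standard error: 2.1 x sqrt(2/61) = 0.38.
- Missing per arm: 5% of 61 is about 3. Protocol 9.4 expects more dropout but gives no new rate. Keeping 58 x 0.95 = 55 evaluable out of 61 means 6 missing (9.8%). Both numbers are assumptions.
- Bound on one arm's mean, endoscopy only: 3 x 3/61 = 0.15, or 6 x 3/61 = 0.30.
- Simulated absolute shift against donor-recipient differences (4,000 trials, equal missingness, placebo endoscopy mean 1.9), with 3 then 6 missing per arm: (a) median 0.03 and 0.03, 95th percentile 0.08 and 0.12; (b) median 0.02 and 0.03, 95th percentile 0.07 and 0.10.
- If all three subscores come from the donor, the 95th percentile for (a) is 0.21 with 3 missing per arm and 0.30 with 6.

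**The case against.** The strongest reply is that the defining sentence governs. It names matching on MMS and age, and the steps only put it into practice, so a sensible programmer would take donor-recipient differences. Reading (b) is also implausible, because it makes step 3 do nothing. This stands as evidence of intent. It does not supply the formula: the text still does not say that two differences are meant, or that they are summed. A program that follows the words as printed picks poorly matched donors.

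The second reply is that little depends on it. This largely stands. SAP 7.3 and 15.1.2 count these patients as non-responders for remission and response whichever donor is used. SAP 5.2.4 excludes patients without a Week 8 MMS from the per-protocol repeat of the primary analysis. The ANCOVA adjusts for baseline MMS. Much of the simulated shift is the noise of using one donor instead of another: even an SD-scaled version of the intended rule differs from the unscaled one by 0.07 and 0.10 at the 95th percentile.

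Three stronger inferences are tempting and are not supported.
- *The literal rule biases the trial against the active arms.* Reading (a) averages about 0.00 with 6 missing in the active arm and none in placebo. Only (b) has a direction: 0.10 against the active arm for endoscopy alone, or 0.26 if all three subscores are imputed. That split is an assumption, and the endoscopy-only size also rests on the assumed placebo endoscopy mean.
- *A changed subscore measures the harm.* Reading (a) gives a different endoscopy subscore from the intended rule in about 63% of imputations, but a random donor does so in about 65%. The figure shows that the match is lost and nothing further.
- *Even the intended rule matches MMS no better than chance.* The gap is 0.9 against 1.3, so it does better, although age dominates.

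**Conclusion.** The point holds as a drafting error in a pre-specified rule for the primary endpoint. As printed, step 3 contradicts the matching stated in the same section. With the donor's values it matches age worse than a random draw (about 22 years against 14) and MMS no better. With the recipient's values it ignores both and pushes imputed scores upward by an amount the documents cannot fix.

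A reader might go on to infer that the primary analysis was programmed wrongly. The documents do not show this. The SAP's version history records that the SAS code appendix was removed, so no code is available to check, and donor-recipient differences remain the evident intent.

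The likely effect on the primary contrast is small against a standard error of 0.38 and an assumed effect of 1.5. The penalty range and the worked scores follow from the text alone. The age and MMS gaps, the tie counts and the contrast shifts rest on the assumed distributions and missing-data rates. The fix is worth making because the rule should have one meaning before unblinding, not because the result is likely to turn on it.

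**What to change.** Before unblinding, replace step 3 with: *subtract |baseline MMS of the subject with the missing value - baseline MMS of the placebo donor| and |age of the subject with the missing value - age of the placebo donor|.* Then confirm that the program does this. The cost is one line of SAP text and a minor programming check.

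Optional and separate from the error: unscaled, age can cost up to 75 - 18 = 57 points, against 9 - 4 = 5 for MMS and 10 match points, so age dominates. The sponsor may divide each difference by its SD among the placebo donors. In simulation this tightens the mean MMS gap from 0.9 to about 0.2 and loosens the mean age gap from 1.5 to about 4.7 years. It changes the donor in about 53% of imputations, so it is a deliberate choice of weighting and not part of correcting the text.

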7.4. MULTIPLE COMPARISONS/ MULTIPLICITY

No adjustment for multiple comparisons is needed, as closed procedures will be applied in testing each dose level vs placebo. The dose testing will commence with comparing the ABX464 50mg dose with placebo. If this is significant at a 5% two-sided level (i.e. $p < 0.05$) a comparison against placebo will be carried out at the ABX464 100mg dose. Again, if significance at a 5% level for this test is observed the procedure will be repeated at the ABX464 25mg dose. If in this sequence of comparisons of ABX464 dose levels to placebo, one is not significant (i.e., $p \geq 0.05$) the additional comparisons to placebo will not be performed. Should any of the comparisons against placebo be significant, the different dose groups will also be compared, using the same significance level.

Document: \\ieedc-vnasc01\BIOSdata\Abivax\ABX464\FZA92720\Biostatistics\Documentation\SAP\ABX464-103_SAP_V2.0_10MAY2021

Author: [REDACTED] Version Number: 2.0
Version Date: 10May2021

Template No.: CS_TP_BS016 Revision 5

Reference: CS_WI_BS005

Effective Date: 01Apr2018

7.5. EXAMINATION OF SUBGROUPS

Subgroup analyses will be conducted as described in relevant efficacy analysis sections. It should be noted that the study was not designed to detect treatment differences with high statistical power within subgroups.

Analyses will be performed for the following subgroups:

- Gender:

Female

Male

- Age (years):

<30

≥30 to <65

≥65

- Country/Region

Austria	Netherlands
---------	-------------

Belarus	Poland
---------	--------

Belgium	Serbia
---------	--------

Canada	Slovakia
--------	----------

Czech Republic	Slovenia
----------------	----------

France	Spain
--------	-------

Germany	Ukraine
---------	---------

Hungary	United Kingdom
---------	----------------

Italy	US
-------	----

North America (US and Canada).

Western Europe: Italy, France, Germany, Netherlands, Austria, Belgium, Spain, United Kingdom

Eastern Europe: Slovakia, Slovenia, Ukraine, Poland, Czech Republic, Serbia, Hungary, Belarus

- Baseline MMS:

Document: \\ieedc-vnasc01\BIOSdata\Abivax\ABX464\FZA92720\Biostatistics\Documentation\SAP\ABX464-103_SAP_V2.0_10MAY2021

Author: [REDACTED]

Version Number: 2.0
Version Date: 10May2021

Template No.: CS_TP_BS016 Revision 5

Reference: CS_WI_BS005

Effective Date: 01Apr2018

4
5 to 6
7 to 9

- With/without previous biological or JAK inhibitors exposure
- Concomitant UC medications
 - Corticosteroids
 - Immunosuppressants
 - 5ASA

8. OUTPUT PRESENTATIONS

APPENDIX 1 shows conventions for presentation of data in outputs. The templates provided with this SAP describe the presentations for this study and therefore the format and content of the summary tables, figures, and listings to be provided by IQVIA Biostatistics.

9. DISPOSITION AND WITHDRAWALS

All patients who provide informed consent will be accounted for in this study. The number and the percentages of patients enrolled and included in each of the analysis sets, as well as reasons for exclusion from each of the analysis sets, will be tabulated. In addition, the number of screen and baseline failures, as well as discontinued patients with their reason for treatment discontinuation will be tabulated. Protocol deviations will be reviewed and classed as critical, major or minor during the BDR meeting and listed as such.

Listings will include assigned treatment, completion or early discontinuation, and the reason for early discontinuation for each patient, as well as details of protocol deviations, screen and baseline failures and inclusion/exclusion criteria not met, analysis sets and enrolment in the maintenance study (ABX464-104). A cumulative incidence plot of time to discontinuation by study treatment will also be provided.

Document: \\ieddc-vnasc01\BIOSdata\Abivax\ABX464\FZA92720\Biostatistics\Documentation\SAP\ABX464-103_SAP_V2.0_10MAY2021

Author: [REDACTED] Version Number: 2.0
Version Date: 10May2021

Template No.: CS_TP_BS016 Revision 5

Reference: CS_WI_BS005

Effective Date: 01Apr2018

10. DEMOGRAPHIC AND OTHER BASELINE CHARACTERISTICS

Demographic data and other baseline characteristics will be presented for the FAS and PPAS and summarized by treatment arm. No statistical testing will be carried out for demographic or other baseline characteristics.

The following demographic and other baseline characteristics will be reported for this study:

- Age (years)
- Gender
- Country/Region
- Weight (kg)
- Height (cm)
- Body Mass Index (kg/m²)
- Tobacco usage (number of packs per year)
- Baseline MMS
- With/without previous biological or JAK inhibitors exposure (Refractoriness)
- Concomitant UC medication
- UC history (Time since diagnosis of ulcerative colitis (years), Disease Extent)

10.1. DERIVATIONS

10.1.1. BODY MASS INDEX (BMI)

- Body Mass Index (BMI) (kg/ m²) = weight (kg)/height (m)²

10.1.2. TIME SINCE STOPPING TOBACCO USAGE (FORMER SMOKERS)

Time since stopping tobacco usage is determined from date of stopping to date of IC.

Document: \\ieedc-vnasc01\BIOSdata\Abivax\ABX464\FZA92720\Biostatistics\Documentation\SAP\ABX464-103_SAP_V2.0_10MAY2021

Author: [REDACTED] Version Number: 2.0
Version Date: 10May2021

Template No.: CS_TP_BS016 Revision 5

Reference: CS_WI_BS005

Effective Date: 01Apr2018

If the full date of tobacco stop date is available, then:

- Time since stopping tobacco usage (years) = (Date of IC – Tobacco stop date + 1)/365.25

If only the year and month of tobacco stop date are available, the date will be imputed using first day of the month.

If only the year of tobacco stop date is available, the day and month from the IC date will be used to impute the tobacco stop date.

10.1.3. NUMBER OF PACKS PER YEAR

For Current and Former smokers, number of packs is determined as follows:

- If Frequency = Per day, then Number of packs/year = Amount as indicated * 365.25.
- If Frequency = Per week, then Number of packs/year = (Amount as indicated / 7) * 365.25
- If Frequency = Occasional, Number of packs used occasionally = Amount as indicated.

10.1.4. TIME SINCE DIAGNOSIS OF ULCERATIVE COLITIS

Duration of the disease will be calculated from the date of disease onset to the date of IC.

If the full date of disease onset is available, then:

- Time since diagnosis (years) until IC = (Date of IC – Date of onset of ulcerative colitis +1) / 365.25

If only the year and month of date of disease onset are available, the date will be imputed using first day of the month.

If only the year of date of disease onset is available, the day and month from the IC date will be used to impute the onset date.

Document: \\iedc-vnasc01\BIOSdata\Abivax\ABX464\FZA92720\Biostatistics\Documentation\SAP\ABX464-103_SAP_V2.0_10MAY2021

Author: [REDACTED]

Version Number:
Version Date:

2.0
10May2021

Template No.: CS_TP_BS016 Revision 5

Reference: CS_WI_BS005

Effective Date: 01Apr2018

11. SURGICAL AND MEDICAL HISTORY

The medical history information including procedures will be listed for the SAF analysis set. Conditions or procedures which stop prior to or at screening will be recorded. Any other medical condition or procedure occurring after screening will be recorded as an adverse event.

Medical History will be coded using the latest version of the Medical Dictionary for Regulatory Activities (MedDRA) (currently version 23.0). Data captured on the Medical and Procedure History pages of the eCRF will be listed by patient and Medical History will include System Organ Class (SOC) and Preferred Term (PT) coding.

12. PRIOR AND CONCOMITANT MEDICATIONS

Concomitant medications will be summarized and listed for the SAF and coded using the latest version of the World Health Organization Drug Dictionary (WHODD) Global version (currently WHODD Global March 2019 B3) and Anatomical Therapeutic Chemical (ATC) system. Prior and concomitant medications will be listed.

- ‘Prior’ medications are medications which started and stopped prior to the first dose of study medication.
- ‘Concomitant’ medications are medications which started prior to, on or after the first dose of study medication, but on or before the last dose of study medication, and ended on or after the date of first dose of study medication or were ongoing at the end of the study.

See APPENDIX 3 for handling of partial dates for medications. In the case where it is not possible to define a medication as prior or concomitant, the medication will be classified by the worst case; i.e. concomitant.

Document: \\ieddc-vnasc01\BIOSdata\Abivax\ABX464\FZA92720\Biostatistics\Documentation\SAP\ABX464-103_SAP_V2.0_10MAY2021

Author: [REDACTED]

Version Number:
Version Date:

2.0
10May2021

Template No.: CS_TP_BS016 Revision 5

Reference: CS_WI_BS005

Effective Date: 01Apr2018

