6.9. Prior and Concomitant Medication

6.9.1. Allowed concomitant treatment

Allowed Concomitant Medications are:

- Corticosteroids at stable dose of prednisone or prednisone equivalent ≤ 20 mg/day; beclomethasone dipropionate (≤ 5 mg/day) or budesonide MMX (≤ 9 mg/day);
- Oral 5-aminosalicylic acid at stable dose;
- Immunosuppressants in the form of azathioprine, 6-mercaptopurine, or methotrexate at stable dose;
- Antidiarrheals (e.g., loperamide, diphenoxylate with atropine) at stable dose.

Potential other concomitant medications should be kept at constant dose during the course of the study and properly reported in the medical file of the patient and the eCRF.

This information should include the name of the medication (international nonproprietary name), daily dosage, duration, indication and the time of last intake before all PK samplings.

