15.1.4.2. Subgroup Analyses

The primary efficacy analysis will be repeated for the subgroups Age, Gender, concomitant UC medications, with/without previous biological or JAK inhibitors exposure and Baseline MMS, as explained in Section 7.5.

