APPENDIX 5. CONCOMITANT UC MEDICATIONS

CATEGORY	ATC Code value of WHODRUG
AMINOSALICYLIC ACID AND SIMILAR AGENTS (5ASA)	A07EC
CORTICOSTEROIDS	A07EA, H02, D07BA, H02AB
IMMUNOSUPPRESSANTS	L04AD, L04AX, L01BB

Document: \\ieedc-vnasc01\BIOSdata\Abivax\ABX464\FZA92720\Biostatistics\Documentation\SAP\ABX464-103_SAP_V2.0_10MAY2021

Author: [REDACTED]

Version Number: 2.0
Version Date: 10May2021

Template No.: CS_TP_BS016 Revision 5

Reference: CS_WI_BS005

Effective Date: 01Apr2018

Statistical Analysis Plan - SAP V2.0 - 10-May-2021

Electronic Signature Manifestation

This page is a manifestation of the electronic signature(s) used in compliance with the organization's electronic signature policies and procedures.

Signer Full Name	Meaning of Signature	Date and Time
[REDACTED]	Document Approval (I certify that I have the education, training and experience to perform this task)	10 May 2021 14:23:18 UTC
[REDACTED]	Document Approval (I certify that I have the education, training and experience to perform this task)	10 May 2021 14:41:50 UTC
[REDACTED]	Document Approval (I certify that I have the education, training and experience to perform this task)	10 May 2021 14:45:57 UTC

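### The concomitant UC medication subgroup has no baseline time point, and the SAP's only definition of concomitant admits drugs started after first dose

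*SAP*

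**What the plan says.** SAP 12 defines concomitant medications as "medications which started prior to, on or after the first dose of study medication", with the limits "but on or before the last dose of study medication, and ended on or after the date of first dose of study medication" or ongoing at study end. Where a medication cannot be classified, "the medication will be classified by the worst case; i.e. concomitant". Treatment runs for 16 weeks, so this window extends well past the Week 8 endpoint.

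The same term then names a subgroup. SAP 7.5 lists "Concomitant UC medications" with three categories: corticosteroids, immunosuppressants and 5ASA. SAP 15.1.4.2 states: "The primary efficacy analysis will be repeated for the subgroups Age, Gender, concomitant UC medications", among others. Appendix 5 identifies the categories by "ATC Code value of WHODRUG" and gives no dates.

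SAP 10 includes concomitant UC medication in the list introduced by "The following demographic and other baseline characteristics will be reported for this study", again without a timing rule. SAP 6.2 treats a concomitant medication that begins on the day of first dose as post-baseline.

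**The concern.** Other than the Appendix 3 algorithm that applies it to incomplete dates, Section 12 is the only definition of concomitant in the SAP. A programmer who combines the Section 12 flag with the Appendix 5 codes would put a patient who first takes a steroid in Week 6, or in Week 12, into the corticosteroid subgroup. The SAP 10 row would count that patient as a user at baseline.

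If patients who are doing poorly are more likely to start such a drug, and poor outcomes are commoner on placebo, membership depends on outcome and differs by arm. Removing poor responders from the non-user group raises its placebo mean more than its active mean, and adding them to the user group does the reverse. The effect then looks smaller without background therapy and larger with it, even if it is the same in everyone. Whether the drug works with or without steroids or immunosuppressants is a result that readers are likely to use.

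**Working it through.** **1. Inputs from the plan.** Protocol 9.4 gives mean MMS reductions of 2.5 (ABX464) and 1.0 (placebo), SD 2.1, 5% dropout, 58 per arm and later 61. As a check on these inputs: 58 × 0.95 ≈ 55 evaluable per arm gives 96.0% power per comparison (two-sample t) and, by simulation, 90.4% for passing all three ordered tests. This agrees with the stated power above 90% and the total of 232. Nothing below changes these figures.

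**2. Assumptions, not in the documents.** The true effect is 1.5 in every patient. A share b = 0.40 of patients use the drug at baseline. A share p of baseline non-users starts it on study. The plan gives neither b nor p.

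**3. Worst-case sorting.** Exactly the worst p of non-users start. With z = Φ⁻¹(p):

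- mean of starters, m = μ − σφ(z)/p
- mean of remaining non-users = μ + σφ(z)/(1 − p)
- mean of users = [bμ + (1 − b)p·m] / [b + (1 − b)p]

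Placebo, p = 0.10, φ(z) = 0.1755:

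- starters 1.0 − 2.1 × 0.1755/0.10 = −2.69
- remaining 1.0 + 2.1 × 0.1755/0.90 = 1.41
- users (0.40 × 1.0 − 0.06 × 2.69)/0.46 = 0.52

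Active, p = 0.04, φ(z) = 0.08617:

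- starters 2.5 − 2.1 × 0.08617/0.04 = −2.02
- remaining 2.5 + 2.1 × 0.08617/0.96 = 2.69
- users (0.40 × 2.5 − 0.024 × 2.02)/0.424 = 2.24

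Effect in non-users: 2.69 − 1.41 = 1.28. Effect in users: 2.24 − 0.52 = 1.72. The gap is 0.44 on the rounded figures.

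**4. Milder sorting.** Starters are a random share q of non-users whose reduction is below 1 point. That group is Φ(0) = 50% of placebo and Φ(−1.5/2.1) = 23.75% of active non-users. With q = 0.20 the start rates are 10% and 4.75%, and the starters' means are −0.68 and −0.23.

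- Non-users: placebo (1.0 + 0.10 × 0.68)/0.90 = 1.19; active (2.5 + 0.0475 × 0.23)/0.9525 = 2.64; effect 1.45
- Users: placebo (0.40 − 0.06 × 0.68)/0.46 = 0.78; active (1.0 − 0.0285 × 0.23)/0.4285 = 2.32; effect 1.54

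**5. Results for b = 0.40.**

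| Sorting | Starts, placebo / active | Effect, non-users | Effect, users | Gap |
|---|---|---|---|---|
| Worst case | 10% / 4% | 1.28 | 1.72 | 0.44 |
| Worst case | 5% / 2% | 1.38 | 1.65 | 0.28 |
| Worst case, equal starts | 5% / 5% | 1.50 | 1.50 | 0 |
| Mild, q = 0.20 | 10% / 4.75% | 1.45 | 1.54 | 0.09 |
| Mild, q = 0.10 | 5% / 2.4% | 1.48 | 1.52 | 0.04 |
| Membership fixed at first dose | none counted | 1.50 | 1.50 | 0 |

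**6. Against sampling error.** 61 × 0.95 ≈ 58 evaluable per arm, so about 23.2 users and 34.8 non-users. The standard errors of the two contrasts are 2.1√(2/23.2) = 0.617 and 2.1√(2/34.8) = 0.503. For the gap it is √(0.617² + 0.503²) ≈ 0.80. The worst case is 0.44/0.80 = 0.55 of one standard error.

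**The case against.** A reader might infer that the subgroup is defined by Section 12, and so that the groups are in fact shaped by response. The documents do not go that far.

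- No section ties the subgroup to Section 12, which serves the safety-set summaries and listings. SAP 10 places the variable with baseline characteristics, the other factors listed in SAP 7.5 are baseline factors, and Protocol 3.1.3 counts concomitant corticosteroid treatment among the baseline characteristics that the DSMB watches. A baseline reading is reasonable.
- On-study starts are restricted. Protocol 6.9.1 allows "Immunosuppressants in the form of azathioprine, 6-mercaptopurine, or methotrexate at stable dose", and likewise corticosteroids and oral 5-ASA; Protocol 6.9.2 prohibits the topical forms. Under Protocol 7.2, treatment failures receive standard of care once off study treatment, and drugs started after last dose fall outside the Section 12 window.
- Worst-case sorting assumes that starters are exactly the patients with the poorest Week 8 scores, which is extreme.
- SAP 7.5 itself warns of low power within subgroups, and no interaction test is planned.

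Most of this stands and limits the point. It does not remove it. A baseline heading is not a timing rule, and SAP 3.3 keeps a Week 16 exposure subgroup, so the plan does not confine subgroups to baseline factors. Protocol 7.2 says that failures may be withdrawn, not that they must be, and the FAS does not exclude a patient who starts a drug and stays on study. The per-protocol review of prohibited medication runs only to Week 8, whereas the Section 12 window runs to last dose.

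**Conclusion.** The point holds as a gap in definition. The subgroup and the SAP 10 row have no time point, and the one definition available would let in drugs started after first dose, even after Week 8. If that definition is used, membership can depend on response. The documents do not show that it will, and they give no rate of on-study starts.

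Under the stated assumptions the spurious gap is 0.04 to 0.09 points with mild sorting and reaches 0.44 only with worst-case sorting and unequal starts. With equal start shares in the worst-case model it vanishes. All of these are small against a standard error near 0.80, so the matter is one of valid definition more than of likely large error. The FAS primary analysis, the ordered dose tests, N, alpha and power are untouched. The change is still worth making, because two programmers could produce different tables from the present text.

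**What to change.** State in SAP 7.5, SAP 10 and Appendix 5 that a patient belongs to a UC medication category if a drug with one of the listed codes was started before, and not stopped before, the first dose. This agrees with SAP 6.2, which already treats starts on the day of first dose as post-baseline. Say how incomplete dates are handled for this flag, since the Section 12 default to concomitant is not suited to it; the Appendix 3 imputation of partial dates can be reused. Summarise UC medication started on study separately, by arm and by whether it began before or after Week 8.

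The cost is about one sentence in each place and one derived variable. Start, end and ongoing fields are already on the concomitant medication form, no new data are needed, and the change can be made before unblinding.
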